Child characteristics (Severity, Cognitive, Age, Health) will be recorded, respectively, from a Severity Index, Bayley III scores, and a Demographic questionnaire and Health questionnaire, which are both completed by parents. Environmental factors include: 1) Parent/child interaction (PCI-DMC) See Figure 1, Appendix C., 2) Home environment (HOME scale [Elardo & Bradley, 1981]), 3) Socioeconomic status (SES), 4) program attendance/participation (visit counts), and 4) overall amount of services (Therapy Services questionnaire). The Home Observation for Measurement of the Environment (HOME) Inventory – Infant/Toddler version assesses the home environment including adult/child contact, social/cultural experiences, physical environment, and access to toys. SES will be measured on a Demographic questionnaire completed by parents. Program attendance will be recorded by the number of accomplished visits, documented by the therapist visiting the home. Amount of therapy recorded on the Therapy Service questionnaire completed by parents(Appendix C).

Our fidelity approach will determine the degree to which all elements of the START-Play intervention are delivered across treatment and control conditions (Knoche et al, 2010). We will assess dosage, adherence, quality, participant responsiveness, and program differentiation (Berkel et al., 2011; Cordray & Pion, 2006; Dane & Schneider, 1998; O’Donnell, 2008) with three primary measures: (1) START-Play Home Visit Coding Guide (adapted from the Home Visit Observation Form; McBride & Peterson, 1997) (see Appendix C); (2) Therapy Services Form (adapted from Westcott & Effgen, 2011; Appendix C); and (3) Home Activity Log (Appendix C). Both the experimental and control groups will be measured using these instruments.

5. Sample selection and size

Infants (n=42) with neuromotor disorders will be randomly assigned to either the experimental intervention (START-Play Intervention) or to a control group between 7-16 months of age depending on motor skill readiness for sitting and reaching activities. We expect a 10% drop-out rate in this longitudinal study, for a final number of 38 children at our site, 19 in each group. Power analysis was conducted for this multi-site trial on pilot data for each variable, and N=152 (4 sites, 38 each), with 93%-99% ability to detect true difference in our primary variable.

Inclusion criteria:

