- The demographics of the regions combined are representative of the US as a whole (average of 4 recruitment sites within 2% of US average for % racial distribution/economic status).
- This project requires experienced primary investigators at each site in order to evaluate, disseminate and expand to other sites around the US in a follow-up project. The team assembled for this project includes the best pediatric early intervention motor and cognitive team that the United States has to offer.
- The assembled team has a proven track record of recruitment/retention for early intervention and family engagement, and strong publication and teaching records for dissemination.

Retention

Attrition is expected to be approximately 10% based on our previous studies; therefore, we plan to recruit 152 infants/families to accommodate dropouts and have 140 complete the study. Strategies to reduce attrition include small honoraria and gifts for participants, intervention and measurement all provided in the home, and flexibility in scheduling to accommodate each family's needs. In addition, thank you notes and gift cards will be provided to the family upon completion of the intervention and each of the follow-up assessments. Our power analyses have considered

this level of attrition and our statistical techniques account for missing data, thus ensuring our ability to complete the complex modeling analyses proposed. If a child is not tracked through the end of the follow-up period or assessment periods are missed but the child remains in the trial, we will utilize full information maximum likelihood (FIML) estimation as a missing data procedure to allow an Intention to Treat (ITT) perspective. Little's (1988) MCAR test and Simonoff's (1988) regression diagnostic procedures will be conducted to determine if missing observations or participant non-response meet the Missing Completely at Random (MCAR) or Missing at Random (MAR) assumptions required by the proposed statistical procedures. Missing data assumed to be at least MAR will be dealt with through FIML without list-wise deletion or imputation methods (Enders, 2001).

ii. Research Hypotheses:

PRIMARY HYPOTHESES

Hypothesis 1: Compared to the BAU group, the START-Play group will show greater improvements from pre- to post- intervention (short-term effect) in:

- a. sitting Variable: Gross Motor Function Measure (GMFM) sitting scores
- b. reaching Variable: Number of toy contacts

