- **iv. Power**
- Sample Size: Each of the 4 sites will recruit 38 infants (total $N=152$) to retain 35 infants for a total of $N = 140$ infants in the study. The initial ($N=152$) and retained ($N=140$, $n=70$ per condition) sample sizes were chosen according to feasibility of recruitment in each site as well as considerations of time and resources needed for a 4-year study.
- Power analysis for Primary Hypotheses 1 & 2: We used a simulation-based power analysis (Muthén & Muthén, 2002; Theommes et al, 2010) to estimate the power for the randomized trial with repeated measures design as evaluated with the proposed Linear mixed modeling (LMM; Laird & Ware, 1982; Wallace & Green, 2002) utilizing FIML for attrition-based missing data. *Mplus* was used for simulations and empirical analyses. Simulations were based on detecting significance in the treatment by time interaction during the intervention phase, γ_{11} . The analysis assumed a small intraclass correlation for the slope across infants (e.g., small variance of the treatment effect of 0.05; Raudenbush & Liu, 2000), a two-tailed nominal error rate of $\alpha = .05$, an initial sample size of 152 infants at baseline, and an attrition scenario of 10% loss by the end of the 3-month intervention (based on patterns observed in previous research conducted by the collaborative team). We conducted the power analysis essentially in support of Hypothesis 1 (the short-term effect at the end of the intervention phase) based on the position that Hypothesis 2 will be supported if the initial effect is then at least sustained through the follow-up period which would be evidenced by a non-significant γ_{21} parameter (no differential change). Prior published research by [name] et al. (2010) and Heathcock et al. (2008) were used to derive effect size estimates for sitting (GMFM, $d=1.21$) and reaching (toy contacts, $d=1.32$), respectively. Pilot data from [name] & [name] and [name] were used to derive

effect size estimates for global development (Bayley III, $d=0.43$) and problem solving (IGDI, $d=1.11$), respectively.

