In this randomized trial, we propose a repeated measures design where individual children serve as the unit of randomization. This experimental study will involve up to 38 children from each of 4 geographic sites resulting in up to 152 total participants. Participating children will be assessed on up to 6 unevenly spaced occasions per the assessment schedule in Table 2 with the metric of time being the number of months since the beginning of the study. Linear mixed modeling (LMM; Laird & Ware, 1982; Wallace & Green, 2002) is an appropriate approach in this study due to presumed individual child differences in rate of change and correlated outcomes due to hierarchical nesting, the uneven spacing of measurement occasions, and the potential for missing data due to attrition. The same fundamental model will be used in simultaneously testing Hypotheses 1 and 2, with models differing only in the particular outcome included in the model. Hypotheses 3 and 4 will require parallel process growth modeling (see Cheong et al., 2003), which is a synthesis of LMM and structural equation modeling (SEM). The discussion of analytic methods for Hypotheses 1 and 2 will be presented in a LMM format, and the discussion for Hypotheses 3 and 4 will be in SEM format. SAS PROC GLIMMIX (currently v13.1) will be used for LMM analyses, and Mplus (currently v7.2) used for SEM analyses.

Prior to evaluation of specific study aims and hypotheses, all variables at all measurement occasions will be described by numeric summaries and visual displays (such as histograms and boxplots) to assess for normality and test other prerequisite modeling assumptions.

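### The protocol's 93%-99% power leaves out the Bayley III (48% in the SAP), 38 per site and 152 are after dropout in the protocol but recruited in the SAP, and two SAP model-fit powers appear transposed

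*Protocol*

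**What the plan says.** **Power.** Protocol section 1 lists four primary outcomes under Hypotheses 1 and 2: GMFM sitting, toy contacts, IGDI problem solving and the Bayley III. Section 5 states "Power analysis was conducted for this multi-site trial on pilot data for each variable", and the same sentence ends with "N=152 (4 sites, 38 each), with 93%-99% ability to detect true difference in our primary variable". It gives no figure for any single outcome.

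SAP section iv gives the following for the group difference in slopes during the intervention, with 152 at baseline and two-sided alpha .05:

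| Outcome | Planned d | Stated power | Stated detectable d |
|---|---|---|---|
| Sitting (GMFM) | 1.21 | >99% | 0.48 |
| Reaching (toy contacts) | 1.32 | 93% | 0.66 |
| Problem solving (IGDI) | 1.11 | >99% | 0.56 |
| Global development (Bayley III) | 0.43 | 48% | 0.64 (at 80% power) |

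**Headcount.** Protocol section 5: "Infants (n=42) with neuromotor disorders will be randomly assigned to either the experimental intervention" and "We expect a 10% drop-out rate in this longitudinal study, for a final number of 38 children at our site". SAP section i (Retention): "we plan to recruit 152 infants/families to accommodate dropouts and have 140 complete the study", with expected attrition of about 10%. SAP section iv: "Each of the 4 sites will recruit 38 infants (total $N=152$) to retain 35 infants"; its simulation used "an initial sample size of 152 infants at baseline, and an attrition scenario of 10% loss by the end of the 3-month intervention". SAP section ix: "This experimental study will involve up to 38 children from each of 4 geographic sites resulting in up to 152 total participants".

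**Model fit.** SAP section iv gives close-fit power of >.99 for Hypothesis 3 (df=51) and .96 for Hypothesis 4 (df=115). Both use N=152, RMSEA 0.05 against 0.10, and alpha 0.05.

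**The concern.** The protocol's range is worded as if it covered every variable, yet it matches three of the four primary outcomes and omits the weakest. Global development is the trial's stated end goal and the outcome in the mediation hypothesis. Someone with only the protocol would not learn that the planned Bayley effect has roughly even odds of being detected, and could over-interpret a null Bayley result.

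The headcount conflict is practical. The site is given 42 to randomise in one document and a ceiling of 38 in the other, and 152 means completers in one and recruits in the other.

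The model-fit pair is a matter of internal consistency: with everything else equal, the model with more degrees of freedom is given the lower power.

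**Working it through.** **1. Power range.** Inputs are the planned and detectable d values from SAP section iv. At two-sided .05 on the normal scale, 80% power needs a noncentrality of 1.960 + 0.842 = 2.802. If the standard error does not depend on the effect, power at the planned d is Φ(2.802 × planned d / detectable d − 1.960).

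- Bayley III: 0.43/0.64 = 0.672; 2.802 × 0.672 = 1.882; power 46.9%. The SAP prints 48%, so its two Bayley figures agree to about one point.
- The simulation itself cannot be rerun, because the documents do not give all the variance components.

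Across all four primary outcomes the SAP's own range is therefore 48% to >99%, not 93%-99%.

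**2. Headcount.**

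| | Protocol section 5 | SAP sections i, iv and ix |
|---|---|---|
| Entered per site | 42 | 38 (a ceiling in section ix) |
| Remaining per site | 38 | 35 |
| Meaning of 152 | 4 × 38 after dropout | 4 × 38 recruited |
| Total entered | 4 × 42 = 168, if every site does the same | 152 |
| Total remaining | 152 | 140 |

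- Protocol: 42 × 0.9 = 37.8, or 38, so its 38 is after dropout.
- SAP: 140/152 = 0.921, a loss of 7.9%. A 10% loss would leave 152 × 0.9 = 136.8, about 137.

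Does the headcount explain the low Bayley power? Take all 152 as completers. The noncentrality then rises by at most √(152/136.8) = 1.054.

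- From 46.9%: 1.882 × 1.054 = 1.984, power 51%.
- From 48%: 1.910 × 1.054 = 2.013, power 52%.

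These are upper bounds, because full-information maximum likelihood already uses part of the dropouts' data. The headcount does not account for the gap.

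**3. Close-fit power.** The fit statistic is noncentral chi-square with λ = (N − 1) × df × RMSEA². The critical value is the 95th percentile at RMSEA 0.05, and power is the upper tail beyond it at RMSEA 0.10. With N=152:

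| df | λ at 0.05 | λ at 0.10 | Critical value | Power | Printed |
|---|---|---|---|---|---|
| 51 | 151 × 51 × 0.0025 = 19.25 | 151 × 51 × 0.01 = 77.01 | 93.56 | 0.965 | >.99 |
| 115 | 151 × 115 × 0.0025 = 43.41 | 151 × 115 × 0.01 = 173.65 | 192.78 | 0.9998 | .96 |

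Neither printed value is reproduced. Power rises with df when N and the RMSEA values are fixed (0.965 at 51, 0.982 at 60, 0.996 at 80, 0.9998 at 115), so the printed order cannot occur. Using N in place of N − 1, N=140, other alpha levels, other alternatives and other forms of the test did not give the printed pair. Exchanging the two printed powers reproduces both.

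**4. Reaching (a question only).** The ratio is 1.32/0.66 = 2.00. If 0.66 is an 80% point with the same standard error at both effects, the noncentrality at d=1.32 is 5.603 and power exceeds 99.9%, against 93% printed. The SAP states the 80% target outright only for the Bayley III.

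**The case against.** **The SAP already discloses the 48%, and the protocol is a summary form that points to a fuller proposal.** This stands in part. Nothing is hidden across the two documents together, and neither assigns 93%-99% to the Bayley III by name. But a range introduced as covering each variable, in a document with four primary outcomes, will be read as covering all four. The singular noun at the end of the sentence does not help, since no single primary variable is named.

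**The 42 may be a local over-recruitment allowance.** The protocol presents 38 as what remains after dropout and builds 152 from it, while SAP section ix allows no more than 38 per site. The two do not fit together.

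**The headcount hardly affects power.** That is correct: Bayley power stays at or below about 52% on either reading. The SAP's simulated loss (to about 137 by month 3) is also slightly harsher than its retained 140, so its power is not flattered on this account.

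**A reader might infer that the mediation models lack power for model fit, or that df or N is wrong.** The documents do not support that. A transposition is the simplest explanation, and both recomputed powers exceed .96.

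**A reader might infer that the reaching simulation is wrong.** That goes too far. The conflict rests on 0.66 being an 80% point and on a constant standard error. Sitting and problem solving barely test those assumptions, because any ratio of planned to detectable d above about 1.53 gives >99%. Only the Bayley III tests them, and one approximate match (46.9% against 48%) does not settle the matter.

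**Conclusion.** Wrong as written, on stated power and sample-size figures.

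- **Power range:** the protocol omits a primary outcome with 48% power at its planned effect. This rests on the SAP's own printed figures.
- **Headcount:** 38 per site and 152 carry two meanings (42 or 38 randomised, 38 or 35 retained per site). The SAP's own 152 to 140 is a 7.9% loss beside a stated 10%.
- **Close fit (minor):** the pair is impossible as printed at a common N, alpha and RMSEA values. The recomputed 0.965 and 0.9998 assume that the printed df are right. The conclusion of adequate model-fit power is unchanged.
- **Reaching:** an open question, not an established error.

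None of this shows that the design or an analysis is invalid.

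**What to change.** 1. In Protocol section 5, replace the range with power per outcome, including 48% at d=0.43 and 80% at d=0.64 for the Bayley III.
2. Use one recruited and one retained number, per site and in total, in both documents, with the sponsor to state which. Align the stated attrition with them: 152 to 140 is 7.9%, and 10% leaves about 137.
3. In SAP section iv, confirm the df for the two model-fit calculations and, if they are right, swap the two powers.
4. Ask which power target lies behind d=0.66 for reaching, and confirm the 93% at d=1.32. If either changes, carry it into the protocol.

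Cost: items 1 and 3 are wording and a check. Item 2 is wording only if 152 stays the recruited number, since the SAP's printed power can then stand. Any other number means rerunning the simulations for the four outcomes, though the effect should be small. Item 4 needs a look at the existing reaching simulation. The downside is less favourable stated power for the Bayley III in the protocol.

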Efficacy of the START-Play Program for Infants with Neuromotor Disorders

Clinical trial # NCT 02593825

Award # R324A150103

Statistical Analysis Plan

July 17, 2015

i. Sample

Infants with neuromotor disorders will be referred through: early intervention therapists or service coordinators, NICU follow-up clinics, or other sources depending on the specific model of follow up at the various sites. All sites have strong relationships with local sources allowing adequate recruitment (See Resources and Letters of Support Appendix D).

Inclusion criteria:

- Infants enter study between 7-16 months of age, when they are able to prop sit for 3 seconds and maintain their head at least to the level of neutral alignment with their trunk.
- Gross motor delay as reflected in the Bayley III motor subtest >1.0 SD below the mean.
- Neuromotor disorder such as cerebral palsy (CP), or at risk for CP because of extreme prematurity or brain damage that occurred at or around birth, or infants with motor delay of an unspecified origin (no clear diagnosis, but delay as above)
- Eligible infants may meet the U.S. federal criteria for children with disabilities in one of the following categories: *orthopedic impairments, multiple disabilities, other health impairments, or developmental delay.*
- *Minimal movement requirements/Indicators of readiness for change:* Sits with support of arms for 3 seconds after being placed. Exhibits at least some spontaneous movement of arms.

Exclusion

criteria:

- *Medical complications* that severely limit participation in assessments and intervention such as severe visual and congenital/genetic anomalies, uncontrolled seizure disorder.
- Diagnosis other than an unchanging neuromotor disorder (examples: autism, Down syndrome, spinal cord injury, acquired head injury, muscle disorder).
- A child will be excluded if the parents report any of following: 1) if the child has a disability of a progressive nature such as muscular dystrophy; 2) if the child's family plans to move out of the local area within one year from the start of the study; 3) if the child has major surgery planned that might affect physical performance.

Rationale for choosing sites:

- Each site represents a different region of the US: Northwest (UW), northeast (UD), Midwest (Duquesne), and south (VCU).
- The demographics of the regions combined are representative of the US as a whole (average of 4 recruitment sites within 2% of US average for % racial distribution/economic status).
- This project requires experienced primary investigators at each site in order to evaluate, disseminate and expand to other sites around the US in a follow-up project. The team assembled for this project includes the best pediatric early intervention motor and cognitive team that the United States has to offer.
- The assembled team has a proven track record of recruitment/retention for early intervention and family engagement, and strong publication and teaching records for dissemination.

Retention

Attrition is expected to be approximately 10% based on our previous studies; therefore, we plan to recruit 152 infants/families to accommodate dropouts and have 140 complete the study. Strategies to reduce attrition include small honoraria and gifts for participants, intervention and measurement all provided in the home, and flexibility in scheduling to accommodate each family's needs. In addition, thank you notes and gift cards will be provided to the family upon completion of the intervention and each of the follow-up assessments. Our power analyses have considered

this level of attrition and our statistical techniques account for missing data, thus ensuring our ability to complete the complex modeling analyses proposed. If a child is not tracked through the end of the follow-up period or assessment periods are missed but the child remains in the trial, we will utilize full information maximum likelihood (FIML) estimation as a missing data procedure to allow an Intention to Treat (ITT) perspective. Little's (1988) MCAR test and Simonoff's (1988) regression diagnostic procedures will be conducted to determine if missing observations or participant non-response meet the Missing Completely at Random (MCAR) or Missing at Random (MAR) assumptions required by the proposed statistical procedures. Missing data assumed to be at least MAR will be dealt with through FIML without list-wise deletion or imputation methods (Enders, 2001).

ii. Research Hypotheses:

PRIMARY HYPOTHESES

Hypothesis 1: Compared to the BAU group, the START-Play group will show greater improvements from pre- to post- intervention (short-term effect) in:

- a. sitting Variable: Gross Motor Function Measure (GMFM) sitting scores
- b. reaching Variable: Number of toy contacts
- c. problem-solving Variable: IGDI problem-solving score
- d. global development Variable: Bayley III score

Hypothesis 2: Compared to the BAU group, the START-Play group will show greater sustained improvements from pre-intervention to one year since start of intervention (long-term effect) in:

- a. sitting Variable: Gross Motor Function Measure (GMFM) sitting scores
- b. reaching Variable: Number of toy contacts
- c. problem-solving Variable: IGDI problem-solving score
- d. global development Variable: Bayley III score

Hypothesis 3 (Mediation): Improvements in global development will be (at least) partially mediated by improvements in problem-solving as a function of the intervention at the end of the project (long-term proximal effect).

Variables: GMFM scores, toy contacts, IGDI problem-solving and Bayley III scores.

SECONDARY HYPOTHESES

Analysis of moderators

1. *Hypothesis:* Severity of motor impairment will have a significant influence on overall change in IGDI problem-solving, and motor scores, as well as Bayley III scores. Variable: Severity score (see Table 1)

2. *Hypothesis:* Factors external to the child (socialization opportunities [Modified Parent Child Interaction-Dyadic Mini Code scores (Censullo, 1991) (PCI-DMC)], and home environment (HOME Inventory [Bradley, 1993] & SES), will have a moderate effect on change in GMFM, problem-solving, and Bayley III scores.

Further analysis of motor variables

3. *Hypothesis:* The START-Play group will show posture control measures that are closer to normative values than the BAU group from pre to post intervention. This hypothesis tests additional variables quantifying sitting to supplement Primary Hypothesis 1. Variables: Kinematic measures taken from video analysis.

4. *Hypothesis:* Compared to the BAU group, the START-Play Intervention group will show greater improvements in duration of toy contact and object manipulation from pre to post intervention. This hypothesis tests additional variables quantifying reaching to supplement the

Primary Hypothesis 2. Variables: Unilateral and bilateral contact number and duration, and type of contact (i.e. hand open or closed; palmar or dorsal hand surface, manipulation variables).

iii. Research Design

We propose a 3-month randomized trial with repeated measures design plus a nine-month follow-up. The design is longitudinal to best capture changes over time within both the BAU group and the START-Play group, and to distinguish advances in skill due to the specific intervention vs. general development under the usual model. Recruitment of study participants will be continuous throughout the project’s recruitment period, and assignment to condition will occur at the individual child level. It will not be possible to have a control group without intervention because all recruited children will be delayed enough to have mandated early intervention services. The experimental group will receive the START-Play intervention as well as their regular Part C services. Randomization will be stratified by the severity of neuromotor disorder (mild, moderate and severe). This stratification will help to ensure that the intervention groups are balanced. Randomization will be created using a random number generator using blocks of size 4 or 6, and arranged in sealed envelopes by our biostatistician, separately for each site. Numbered group assignment will be dated and faxed to the PI to verify the process.

A scale created in a previous US Dept. of Education NIDRR-funded study of infants with CP helps ensure equal distribution of children with varying severity of neuromotor dysfunction, and has been adapted for this study. The scale is summarized below:

Table 1. Method to Determine Severity of Disorder

Score Received on the Measure	Measures			
	Distribution	Active Movement	MACS	GMFCS
1	1 side	High	1-2	1-2
2	primarily legs	Moderate	3	3
3	all 4 extremities	Low	4	4

Scores from each column are totaled for a final score: 9-12, Severe; 6-8, Moderate; 4-5, Mild.

- Distribution refers to the areas of the body affected by neuromotor dysfunction.
- MACS: Manual Abilities Classification Scale (Hidecker et al, 2009) describes use of the hands and arms
- GMFCS: The Gross Motor Function Classification System (Palisano et al, 1997) classifies a child’s motor involvement on the basis of functional gross motor abilities.

The assessment schedule covers entry month (between 7-16 months of age) and the following 12 months (between 19-28 months of age). Assessments are at Baseline, Intervention (Rx) and Follow-up. Table 2. Assessment Schedule

Assessment number	1	2	3	4	5	6
Timetable (months after study entry)	0	1	2	3	6	12
Sitting Video Reaching Video	Baseline testing prior to intervention	Rx	Mid Rx testing	Final post Rx testing sitting and reaching	Follow-up	Final Follow-up
Standardized Assessment	Bayley III, GMFM, IGDI		GMFM, IGDI	Bayley III, GMFM, IGDI	Bayley III, GMFM, IGDI	Bayley III, GMFM, IGDI

- What: Our primary and secondary measures capture initial impairments and delays in sitting and reaching, and are sensitive to improvements in sitting, reaching and problem solving.
- Where: The natural setting (home) (sitting and reaching video, Bayley, GMFM and IGDI).
- Frequency and Period (Table 2): Measurement visits total 6 over a 12 month period, organized to provide timely assessments without overwhelming families. Repeated measures assess immediate and long term proximal effects on individual and group change over time.
- Who: Blinded, trained assessors who have met criterion standards in assessment procedures (See Appendix C, assessment manual excerpt). The four data collection sites will each send de-identified data videos to a centralized database. Each site has expertise for specific analyses: 1) sitting video data to Duquesne University; 2) reaching data to University of Delaware; 3) IGDI assessment to Virginia Commonwealth University, 4) Reliability for the Bayley and GMFM assessments to the University of Washington, and 5) overall statistical analysis and fidelity management through University of Nebraska Lincoln. The University of Nebraska-Lincoln will create and maintain a secure web-based database interface for all sites to upload finalized data from each site into a central data system, accessible to all collaborators.
- Reliability: Each assessor will be trained and must reach at least 90% agreement criterion with scoring of specifically created videotaped segments of infants for all measures. A second investigator will re-score 20% of the data for each variable to monitor ongoing measurement reliability. For sitting kinematic measures, investigators will be trained to position the infant, monitor behavior etc. to acquire quality data. The sitting kinematic variables are quantified with a mobile video movement measurement application called SIMI Move. A specific, user friendly interface for early infant movement, developed by SIMI Reality Motion Systems, will be available to each site. The sitting measures will be wirelessly sent to the central location, and intra-rater and inter-rater reliability will be assessed across sites to achieve 90% agreement.
- **iv. Power**
- Sample Size: Each of the 4 sites will recruit 38 infants (total $N=152$) to retain 35 infants for a total of $N = 140$ infants in the study. The initial ($N=152$) and retained ($N=140$, $n=70$ per condition) sample sizes were chosen according to feasibility of recruitment in each site as well as considerations of time and resources needed for a 4-year study.
- Power analysis for Primary Hypotheses 1 & 2: We used a simulation-based power analysis (Muthén & Muthén, 2002; Theommes et al, 2010) to estimate the power for the randomized trial with repeated measures design as evaluated with the proposed Linear mixed modeling (LMM; Laird & Ware, 1982; Wallace & Green, 2002) utilizing FIML for attrition-based missing data. *Mplus* was used for simulations and empirical analyses. Simulations were based on detecting significance in the treatment by time interaction during the intervention phase, γ_{11} . The analysis assumed a small intraclass correlation for the slope across infants (e.g., small variance of the treatment effect of 0.05; Raudenbush & Liu, 2000), a two-tailed nominal error rate of $\alpha = .05$, an initial sample size of 152 infants at baseline, and an attrition scenario of 10% loss by the end of the 3-month intervention (based on patterns observed in previous research conducted by the collaborative team). We conducted the power analysis essentially in support of Hypothesis 1 (the short-term effect at the end of the intervention phase) based on the position that Hypothesis 2 will be supported if the initial effect is then at least sustained through the follow-up period which would be evidenced by a non-significant γ_{21} parameter (no differential change). Prior published research by [name] et al. (2010) and Heathcock et al. (2008) were used to derive effect size estimates for sitting (GMFM, $d=1.21$) and reaching (toy contacts, $d=1.32$), respectively. Pilot data from [name] & [name] and [name] were used to derive

effect size estimates for global development (Bayley III, $d=0.43$) and problem solving (IGDI, $d=1.11$), respectively.

- Based on our previously stated assumptions and the cited pilot data and prior research, power analyses suggest that the targeted sample size will be sufficient to detect the reported effects with greater than 80% power for three of the four primary outcomes. With $N=152$ initial participants, power to detect mean group differences in slopes during the intervention period is >99% for sitting, 93% for reaching, and >99% for problem solving. As these three outcomes are estimated to be over-powered based on pilot/cited data, given the projected initial sample size of $N=152$ we would be able to detect effect sizes as small as $d=0.48$ for sitting, $d=0.66$ for reaching, and $d=0.56$ for problem solving. Based on the effect size derived from pilot data, power to detect mean group differences in global development improvement during the intervention period at the $d=0.43$ level is only 48%; however, given the projected sample size, we would be able to detect an effect size of $d=0.64$ with 80% power.
- *Power analysis for Primary Hypotheses 3 & 4:* Continuing to use the variability and mean differences from the cited prior research and pilot data as estimates of paths A and D in Figure 2, we conducted an empirical power analysis based on the SEM model presented in Figure 2 using an initial sample size of $N = 152$ infants, and assuming a moderate correlation between the measures at baseline ($r = .32$, explained variance = 10%). With these assumptions, we will have 80% power to be able to support the hypotheses of partial mediation of intervention-driven change over time in global development by intervention-driven changes in sitting and reaching and problem solving if the standardized parameter estimate of the mediator(s) on change in global development (paths B (Hyp. 3) or $C_1 * C_2$ (Hyp. 4) in Figure 2) is at least $\beta=.237$, which corresponds to a medium effect.
- A complementary power analysis perspective for evaluating Hypotheses 3 and 4 follows MacCallum et al.'s (1996) guidelines for determining adequacy to test the fit of a model, which indicates whether the necessary parameters/effects are being considered. Evaluation of model fit is a prerequisite for evaluating parameters within the model itself. Accordingly, a hypothesis of *close model fit* can be tested by assuming the Type I error rate to be 0.05, a $RMSEA \leq 0.05$ as indicative of *close fit*, and a $RMSEA > 0.10$ as indicative of poor fit. Given the proposed model in Hypothesis 3, $df_{min}=51$, $N=152$, $RMSEA_{null}=0.05$, $RMSEA_{alt}=0.10$, and $\alpha=0.05$, the power to detect close model fit for Hypothesis 3 is >.99. Given the proposed model in Hypothesis 4, $df_{min}=115$, $N=152$, $RMSEA_{null}=0.05$, $RMSEA_{alt}=0.10$, and $\alpha=0.05$, the power to detect close model fit for Hypothesis 4 is .96.
- In summary, the initial sample size of $N=152$ and retained sample size of $N=140$ (70 per group) is appropriate for the study and will likely yield power to test each primary hypothesis at a medium effect size or larger at the $p < .05$ level, with a power of at least .80. The structure of this proposal ensures that we can realistically produce the first randomized efficacy trial of sitting and reaching with young infants within the funding period.

v. Measures [Outcomes]

Rationale for using multiple measures of developmental skills

The use of standardized tests in isolation is not optimal for infants with neuromotor disorders because of the large increments of change in observable motor skills needed to change the score on any one item, and the complexity of child behavior. Furthermore, our research has shown that standardized assessments like the Bayley III focusing on the discrete performance of tasks are not consistent for identifying and classifying delays in the first two years of life and are poorer predictors of future cognition relative to assessments that involve perceptual-motor

exploration and problem-solving ([name], Paul, et al, 2014; [name] & [name], 2013). However, we want a means to relate our primary measures to other developmental studies. Therefore, we are using a blend of standard tests (Bayley III Scales of Infant Development, individual change assessments (Individual Growth and Development Indicators [IGDI]); Gross Motor Function Measure [GMFM]) and video coding measures to quantify our secondary variables for sitting skills and reaching.

Mindful that specific outcomes are considered critical to children becoming active and successful participants across a variety of settings according to the US Department of Education (OSEP), we acknowledge these outcomes as related to our measures: 1) Positive social-emotional skills and social relationships; 2) Appropriate behaviors to meet needs.

The proposed START-Play intervention relates directly to these critical and functional outcomes. The parent-child interaction measure provides information on the child's progress on outcome 1. The problem-solving IGDI and the GMFM provide information on the child's progress on outcome 2. We are also using the secondary measurable outcomes below, which we have used in previous funded studies, to detect small increments of change and quantify progress of skill in sitting and reaching.

Because this is a longitudinal study, the infant's skills in reaching are expected to change considerably. Although we have based our power analysis on toy contacts, we want to completely describe the advances in reaching as the children gain skill. Thus object manipulation, type of hand contact, and other measures will be coded advanced skill.

Specific Measures

1) Primary Measures for Sitting and Reaching

These variables quantify the initial functional delays in these skills and changes during the Intervention and Follow-up periods.

- GMFM sitting section

The Gross Motor Function Measure (GMFM, Russell et al 1993) is the international standard outcome assessment tool for quantifying change in the gross motor abilities of children with neuromotor disorders (inter-rater reliability, $r=.97$, Russell et al 2000). Each sections raw score and % of the section completed increase as abilities improve.

- Number of toy contacts

